## 4.6 Tapering

For each tapering group, the dose taper schedule is determined by the dose stratification on Day -1. Taper schedules were designed to maximize participant comfort during the taper phase regardless of group assignment. Schedules are provided for participants starting at 8 mg, 16 mg, and 24 mg doses (expressed as amount of buprenorphine).

Suboxone 7 Day Taper Regimen #1 (Days 1 through 7)

Sersonionio.	businer buy tuper regimen #1 (buys 1 through 1)							
Study Day	Dose of Suboxone (expressed as amount of buprenorphine)							
	Starting dose of	Starting dose of	Starting dose of					
	buprenorphine = 8 mg	buprenorphine = 16 mg	buprenorphine = 24 mg					
1	8	16	24					
2	6	12	20					
3	6	10	16					
4	4	8	12					
5	4	4	8					
6	2	2	4					
7	2	2	2					

Suboxone 28 Day Taper Regimen #2 (Days 1 through 28)

Study Day	Dose of Suboxone (expressed as amount of buprenorphine)						
	Starting dose of buprenorphine = 8 mg	Starting dose of buprenorphine = 16 mg	Starting dose of buprenorphine = 24 mg				
1-2	8	16	24				
3-5	6	12	20				
6-8	6	10	16				
9-11	6	8	12				
12-14	4	8	10				
15-16	4	6	8				
17-19	4	4	6				
20-22	2	4	4				
23-25	2	2	2				
26-28	2	2	2				

#### **4.7 Administrative Withdrawal**

Participants in the pre randomization, stabilization phase of the study will be administratively withdrawn if they miss one full week (7 consecutive days) of medication at any time. The reason for this administrative withdrawal is that such participants would not have adequate opportunity to stabilize on the appropriate dosage of buprenorphine. Participants who are administratively withdrawn for this reason will be replaced by new participants to provide the required sample of randomized participants.

Participants in the 28 day taper schedule who miss one full week (7 consecutive days of medication) at any time during the taper will be considered to have completed their taper and will not be restarted on study medication. However, such participants may continue to attend all scheduled study visits and will be considered active participants for the purposes of all other study activities and for data analysis. If these participants choose not to continue to attend study visits they will be withdrawn/terminated. The reasons for not resuming the taper on such participants are as follows: 1) participants who have relapsed to illicit opioid use would require re-induction onto buprenorphine. The re-induction would require several days, and it would be difficult then to reestablish them on their protocol dictated taper schedule; 2) participants who have not relapsed to illicit opioid use would be better served clinically to remain off opioid agonist therapy since the ultimate goal is to reduce the buprenorphine dosage to zero, which they have effectively accomplished.

At any time during the study, if any participant misses three consecutive scheduled visits prior to Day 84 (a period of one month), he/she will be terminated (administratively withdrawn) from the study.

Protocol # CTN-0003 Version 7C

If a participant is hospitalized or imprisoned, he or she will be permanently discontinued from study medication and administratively withdrawn if he or she misses one full week of medication (7 consecutive days). Additionally, at any time during the study, a change in medical status that makes it unsafe for a participant to continue participating will result in study medication discontinuation and withdrawal. The Study Termination Report (STR) will reflect the appropriate reason for withdrawal/termination.

Participants who are administratively withdrawn from the study will be referred, by study personnel, to alternative treatments. This may include remaining in treatment at the study site if clinically appropriate.

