## 7.15 Pregnancy Testing (PG)

Female participants will be required to have a negative pregnancy test (PG) prior to induction and monthly thereafter while receiving Suboxone. Buprenorphine is a Pregnancy Category C Drug. Female participants will also be expected to practice acceptable birth control. Women who become pregnant any time prior to day 7 or 28 (depending on randomization group assignment) will be withdrawn from the study and given immediate access to methadone maintenance services at the CTP or another local treatment provider. Participants refusing methadone maintenance will be referred to another local provider, preferably one providing specialized services for pregnant or post-

Protocol # CTN-0003 Version 7C

partum women. Results of the pregnancy test performed every 4 weeks (Days - 42, -28, 0, 28), will be recorded on the Clinic Visit CRF.

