#### 9.3 Intent-to-Treat and Evaluable Populations

The main intent-to-treat population is defined as the participants who are randomized to a tapering schedule at the end of the 28 day induction and stabilization. The evaluable participant population is defined as participants who are randomized and who complete the tapering schedule without being administratively withdrawn. Parallel analyses will be conducted on these two populations, and their results compared, to assess the impact of completion status on the results.

Protocol # CTN-0003 Version 7C

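### The three-missed-visits rule in Section 4.7 can remove the primary urine visit only in the 28-day arm, and a completed-taper label given only to that arm leaves the evaluable population unevenly defined

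*Protocol*

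**What the plan says.** **Termination for missed visits.** Section 4.7 applies to both arms: at any time in the study, a participant who "misses three consecutive scheduled visits prior to Day 84 (a period of one month), he/she will be terminated (administratively withdrawn) from the study".

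**Deemed completion.** The same section says that a 28-day participant who goes without medication for seven days running "at any time during the taper will be considered to have completed their taper and will not be restarted on study medication". These people may keep attending all scheduled visits and "will be considered active participants for the purposes of all other study activities and for data analysis". They are withdrawn only if they choose to stop attending. No equivalent is written for the 7-day arm.

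**Evaluable population.** Section 9.3 makes the main intent-to-treat population everyone randomized. The evaluable population is "participants who are randomized and who complete the tapering schedule without being administratively withdrawn". The two are analysed in parallel to judge the effect of completion status.

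**Primary outcome and its visit.** Section 9.2 sets the primary outcome as an opiate-free urine the day after the taper ends. Sections 4.2 and 4.9 place that visit at Day 8 for the 7-day arm and Day 29 for the 28-day arm, each with three further days allowed.

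**Early dropout.** Section 4.11 schedules a termination visit. The termination column of Table 1 includes a urine drug screen.

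**The concern.** The termination rule reads as neutral between arms, but the primary visit falls at different points in the visit sequence. If termination closes the remaining visits, the protocol itself can leave the only primary outcome uncollected, and before the primary visit it can do so in one arm only. A statistical analysis plan can say how a missing urine is handled but cannot recover one that was never taken.

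The deemed-completion rule raises a different problem. Section 9.3 uses completion to define a comparison population. If early stoppers may carry the completed label in one arm and have no defined status in the other, the parallel analysis compares differently selected groups and cannot cleanly answer the question set for it.

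**Working it through.** **1. Scheduled visits between randomization and the primary urine (Schema; Sections 4.2 and 4.9)**

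| Arm | Visits after Day 0 and before the primary urine | Primary urine |
|---|---|---|
| 7-day | none (0) | Day 8, window to Day 11 |
| 28-day | Days 7, 14, 21 (3) | Day 29, window to Day 32 |

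Everyone randomized attended Day 0 (or its three-day window), so the run of missed visits starts afresh there. Three consecutive misses can therefore precede the primary urine only in the 28-day arm.

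**2. When the rule acts.** Counted in visits, the third miss is established when the Day 21 visit window closes, so termination falls at about Day 21-22. If the one-month gloss governs, counting 28 to 31 days from Day 0 gives about Day 28-31, which overlaps the Day 29-32 window. The text does not say which reading applies, so sites could act differently.

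**3. How the two rules meet.** The visit table allows at most seven days of medication at Day 0. A 28-day participant who then misses Days 7, 14 and 21 has gone seven days without medication by about Day 14 and is deemed to have completed the taper. About a week later the same person is administratively withdrawn. Section 9.3 requires completion without administrative withdrawal, so this person carries both labels.

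**4. The plan's own power figure (Section 9.6).** Inputs: 20% versus 32%, 240 per arm, two-sided 5% (Section 9.4). For a two-proportion normal test with continuity correction:

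z = (d − c − 1.96·SE0) / SE1, where c = (1/n1 + 1/n2)/2, SE0 uses the pooled proportion and SE1 the separate proportions.

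- Pooled proportion = 0.26; SE0 = √(0.26 × 0.74 × 2/240) = 0.0400
- SE1 = √((0.20 × 0.80 + 0.32 × 0.68)/240) = 0.0397; c = 1/240 = 0.0042
- z = (0.12 − 0.0042 − 0.0785)/0.0397 = 0.94, power **82.7%** (stated: about 82%)

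With 192 per arm (20% dropout) the same formula gives 72.9% (stated: 72%). Without the correction the results are 85.2% and 76.6%, so the corrected form is the one that matches.

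**5. Illustration of one-sided loss.** The protocol gives no rate, so L is an assumption: the share of the 28-day arm lost through the rule, at random with respect to the true result. The 7-day arm loses nobody to it.

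| L | People (of 240) | 28-day rate if counted positive, 0.32 × (1 − L) | Power, counted positive | Power, dropped (n2 = 240 × (1 − L)) |
|---|---|---|---|---|
| 2% | 4.8 | 31.4% | 78.5% | 82.3% |
| 5% | 12 | 30.4% | 71.3% | 81.7% |
| 10% | 24 | 28.8% | 57.1% | 80.6% |

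At L = 5%, counted positive: z = (0.104 − 0.0042 − 1.96 × 0.0396)/0.0393 = 0.56, power 71.3%.

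**6. Why these are upper bounds.** Only those who would have come back for Day 29 are lost through the rule; the others would have been missing anyway. If 5% are terminated and a quarter of them would have returned (also an assumption), the rule's own loss is 0.05 × 0.25 = 1.25%. The rate becomes 0.32 × 0.9875 = 31.6% and, counted positive, z = (0.116 − 0.0042 − 1.96 × 0.0399)/0.0396 = 0.85, power 80.2%.

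**The case against.** Several points on the other side stand.

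- A reader might infer that both rules delete primary outcomes. The deemed-completion rule does not: those participants stay on the visit schedule and in the analysis. Sections 4.2 and 4.9 already fix the 28-day end-of-taper visit at Day 29, and nothing moves it earlier for them.
- A reader might infer that all protocol withdrawal before the primary urine is one-sided. It is not. In either arm, "a change in medical status that makes it unsafe for a participant to continue participating will result in study medication discontinuation and withdrawal". A participant in hospital or prison is "permanently discontinued from study medication and administratively withdrawn if he or she misses one full week of medication (7 consecutive days"), which could reach the 7-day arm if all seven doses are missed. Section 7.15 adds: "Women who become pregnant any time prior to day 7 or 28 (depending on randomization group assignment) will be withdrawn from the study".
- A termination urine is scheduled. It is not tied to Day 29, however, and it depends on someone who has just missed three visits attending.
- The one-month gloss need not be a slip. A person last seen on Day 0 who misses three weekly visits is next due about four weeks later. What remains is the doubt over timing.
- Section 9.3 never says that the Section 4.7 label confers evaluable status; completing the tapering schedule could mean taking all 28 days. Nor does any text say how a 7-day participant who stops on Day 2 is classed. A missing seven-day rule in a seven-day taper is also natural, since it would mean taking no doses. This makes the evaluable point an ambiguity to settle, not a proven misclassification.
- Section 9.7 foresees a possible comparison at equal times after randomization. By Day 28 the missed-visits rule can reach both arms, since the 7-day arm can miss Days 8, 14 and 21. But that analysis is post hoc and is not the primary one.

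**Conclusion.** The point holds in a limited form. The three-missed-visits rule can pre-empt the primary visit only in the 28-day arm, three prior visits against none, and its timing is unclear. The deemed-completion rule exists for that arm alone and is not reconciled with the evaluable definition.

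The size is unknown. The power figures rest on assumed loss rates, loss at random, and every lost person otherwise attending Day 29. They bound the rule's effect and do not forecast it.

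A reader might go further and conclude that the rule builds in bias of a known direction. The document does not support that. Counting missing urines as positive works against the 28-day arm, while dropping people who would have been positive works in its favour. The protocol does not state the handling, and a statistical analysis plan may. Either arm can also miss its primary visit without this rule, and the intent-to-treat population keeps everyone randomized.

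This is an inexpensive improvement worth making because it protects collection of the sole primary outcome. It is not a defect that invalidates the design.

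**What to change.** No medication or clinical rule needs to change.

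1. In Section 4.7, state that three missed visits do not end outcome data collection for randomized participants: the end-of-taper, 1-month, Day 84 and 3-month post-taper visits stay open to all. This also removes the effect of the timing doubt on the primary urine.
2. In Section 9.2, confirm that the primary urine for deemed completers remains the scheduled Day 29 visit, as Sections 4.2 and 4.9 already imply.
3. Reconcile Sections 4.7 and 9.3 by defining evaluable with one Dosing Log criterion, applied identically in both arms (for example, the same minimum share of scheduled taper days taken), in place of the completed label.

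The cost is a short amendment, some extra contact attempts, and visit payments that Section 6.0 already provides for.

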## 4.8 Treatment as Usual (TAU)

Since the CTN protocols are designed to occur in "real-life" clinic settings, psychosocial treatment procedures in existence at each CTP will be followed throughout the study. However, in order to assure that a basic platform of participant education is provided to all participants, all CTPs will be provided with self-help buprenorphine treatment booklets for distribution to research participants. This self-help handbook is attached as Appendix III.

## **4.9 Post Taper and 1 Month Follow-ups**

During this phase the following visits will occur and the measures listed in the time and event schedule should be obtained at the appropriate visit:

#### Group 1:

```
Day 8: End of Taper Visit (CV, AE, CM, COWS, ARSW, VAS, SQ, U, DL)
(3 day window - post)

Day 14: Weekly Visit (CV, AE, CM, COWS, ARSW, VAS, U)

Day 21: Weekly Visit (CV, AE, CM, COWS, ARSW, VAS, U)

Day 28: 1 Month Post Randomization Follow-Up
(CV, LFT, PG, AE, CM, COWS, ARSW, VAS, U)

Day 35: 1 Month Post Taper Follow-Up (7 day window - post)
(CV, RBS, PHY, BC, UA, ECG, AE, CM, COWS, ARSW, ASI, VAS, SQ, U)

Day 42: Weekly Visit (CV, AE, CM, COWS, ARSW, VAS, U)

Day 49: Weekly Visit (CV, AE, CM, COWS, ARSW, VAS, U)

Day 56: Weekly Visit (CV, AE, CM, COWS, ARSW, VAS, U)
```

Protocol # CTN-0003 Version 7C

#### Group 2:

```
Day 29: End of Taper Visit and 1 Month Post Randomization Follow-Up (CV, LFT, PG, AE, CM, COWS, ARSW, VAS, SQ, U, DL) (3 day window - post)

Day 35: Weekly Visit (CV, AE, CM, COWS, ARSW, VAS, U)

Day 42: Weekly Visit (CV, AE, CM, COWS, ARSW, VAS, U)

Day 49: Weekly Visit (CV, AE, CM, COWS, ARSW, VAS, U)

Day 56: 1 Month Post Taper Follow-Up (7 day window - post) (CV, RBS, PHY, BC, UA, ECG, AE, CM, COWS, ARSW, ASI, VAS, SQ, U)
```

It should be noted that the total number of visits during stabilization, taper, post taper and follow-up are the same for both groups (however, they occur in different phases, that is group 2 has more taper visits while group 1 has more post taper visits, but the total is identical).

#### **4.10 Three Month Follow-ups**

Each group will attend two separate 3 Month Follow-Up visits, one 3 Month Post Randomization (Day 84) and one 3 Month Post Taper (the end of the taper schedule Days 91 and 112 respectively). The following is the appropriate schedule and measures to be obtained:

## Group 1:

```
Day 84: 3 Month Post Randomization Follow-Up
(CV, AE, CM, COWS, ARSW, VAS, U)

Day 91: 3 Month Post Taper Follow-Up (7 day window - post)
(CV, RBS, COWS, ARSW, ASI, VAS, STR
SQ, U, SAE)
```

## Group 2:

```
Day 84: 3 Month Post Randomization Follow-Up
(CV, AE, CM, COWS, ARSW, VAS, U)

Day 112: 3 Month Post Taper Follow-Up (7 day window - post)
(CV, RBS, COWS, ARSW, ASI, VAS, STR
SQ, U, SAE)
```

#### 4.11 Post Study Options/Early Termination

Upon completion of the tapering phase, or in cases of early dropout, participants may continue in TAU at the CTP or may be referred to available local treatment resources. In the event any participant desires additional pharmacological treatment for their opiate

Protocol # CTN-0003

Version 7C

dependence or if the study staff finds that additional treatment is clinically indicated, the site will refer the participant to a local provider of methadone, LAAM, or buprenorphine. Participants enrolled in Treatment As Usual (TAU), usually psychosocial treatment, at the site will be encouraged to continue participation once the taper is complete, if they have not completed this treatment. Any participant who has completed TAU and desires further psychosocial treatment will be given a referral to a local treatment provider. Treatment received after the taper is complete, either pharmacological or psychosocial will not exclude the subject from further participation in this research protocol. Involvement in additional treatment(s) will be noted in the data and participation in this study will continue as outlined. In case of early drop out, a termination visit will be scheduled and all measures as indicated in the "term" column of the Time and Event schedule should be completed.

## 5.0 Study Medication

Suboxone [BUP/NX-combination tablet]: buprenorphine 2 mg and naloxone 0.5 mg or buprenorphine 8 mg and naloxone 2 mg sublingual tablets are manufactured by Reckitt and Benckiser (Hull, UK) and will be supplied by the approved contractor for the National Institute on Drug Abuse.

## **5.1 Dispensing Study Medication**

Investigational agents will be prescribed, dispensed or administered (furnished) by an individual legally qualified to do so in accordance with state regulations.

Participants receiving Suboxone will be instructed to hold the tablet(s) under their tongue until the tablets have dissolved. Dissolution of tablets will be monitored at each CTP by a nurse, physician or pharmacist, as clinically warranted. Participants will be asked to remain in the clinic, to be observed, for at least one hour on the first day of treatment following the administration of Suboxone. Vital signs will be measured pre and post dose, and participants will be asked not to leave the clinic until vital signs are stable.

## 5.2 Labeling

Study medication will be distributed to investigational sites in bottles of 30 sublingual tablets. Each site will prepare individual prescriptions for each participant visit. These prescriptions will be provided in child resistant packaging and clearly labeled "Investigational Use Only and "Keep Out Of Reach Of Children." This is an open-label study with no blinding of investigational agents.

#### **5.3 Drug Accountability**

Accurate recording of all investigational agents received, dispensed, prescribed or administered, and returned or destroyed will be made.

Protocol # CTN-0003 Version 7C

## **6.0 Participant Compensation**

Participants will be compensated in scrip or cash for their participation in accordance with local IRB requirements. Some sites may be required to compensate participants using scrip. For sites required or electing to use scrip, each CTP can determine what type of scrip is most appropriate (e.g., gift certificates for groceries, department stores, etc.).

Participants will receive \$25 in scrip or cash for the following visits; screening, immediately post taper, and for each of the 1 month post taper, 3 month post randomization and 3 month post taper visits. Participants completing all post taper visits (end of taper, 1 month and 3 month) will receive an extra \$25 in scrip or cash. Participants will receive \$10 in scrip or cash for each of the weekly clinic visits during days 1-56 (not including the end of taper and 1 month post taper visits). There are 6 of these visits for each group. The maximum compensation for participation available to participants in scrip or cash will be \$210 for either group (\$125 for screening and 4 post taper visits, plus \$25 bonus, plus \$60 weekly visits = \$210).

#### 7.0 Measures

#### 7.1 Locator Form

A Basic Locator Questionnaire will be completed at screening and kept confidential and separate from the participant's research records. The Basic Locator Questionnaire will be used to facilitate contact with the participant during the study and follow-up. Participants will be asked to provide locator information including their residential street address and a working telephone number, or an address of a relative if they are homeless, as well as the address and telephone number of a non-drug abusing relative or friend who can reach the participant in emergencies. This information will be updated periodically throughout the study and follow-up.

## 7.2 Demographic Data

Each participant will complete a Demographic Data Form that records information regarding race and ethnicity, age, education, marital status, and employment status.

#### 7.3 Diagnostic and Statistical Manual-IV (DSM-IV)

The DSM-IV Checklist for Substance Dependence is a clinician-rated questionnaire used to determine the participant's dependence on opiates, benzodiazepines, alcohol, amphetamines, cocaine, cannabis, hallucinogens, inhalants and sedatives. The checklist will be completed at screening. This diagnostic tool will be used to determine that the participant currently meets criteria for opiate dependence. Results of this assessment will aide the physician in assessing the potential participant's benzodiazepine use history in order to help determine eligibility to participate.

Protocol # CTN-0003 Version 7C

## 7.4 Clinical/Psychiatric Interview

Each participant will be interviewed by the study physician or other appropriately trained medical staff, prior to enrollment, to determine any possible psychiatric or medical exclusion and to obtain a complete psychiatric history. Qualified examiners will document the presence or absence of psychiatric or medical exclusions in the progress notes, on the inclusion/exclusion form and/or on a Medical/Psychiatric Eligibility Assurance Form (a non-data form).

#### 7.5 Inclusion/Exclusion

Inclusion/Exclusion criteria will be assessed at the conclusion of screening in order to determine a potential participant's eligibility. This form may not be completed until all laboratory results and ECG readings (if applicable) are returned and reviewed at the site.

